9.5.7 Immunogenicity Assessments

9.5.7.1 Surveillance and Laboratory Diagnosis of SARS-CoV-2 Infection during Clinical Trial

During the observation period of the clinical trial, the participants with fever, cough and other respiratory symptoms should immediately go to the designated hospital. The doctor or investigator may collect the nasopharyngeal/throat swabs and to perform CT and other imaging examinations to analyse whether it is caused by SARS-CoV-2 infection. In the event of SARS-CoV-2's infection during the clinical trial, it is necessary to conduct a case investigation, and the critically ill or dead cases need to continue to conduct a special investigation, mainly to analyze whether there is an ADE or VAERD phenomenon. Subjects encountered the medical condition listed in Table 9-5 should also check HLA and SARS-CoV-2 infection,

In addition to SARS-CoV-2 nucleic acid detection, multiple pathogens will be detected for differential diagnosis of swabs. The detail of detectable pathogens of test kit will be listed below:

- ✓ Adenovirus
- ✓ Coronavirus 229E
- ✓ Coronavirus HKU1
- ✓ Coronavirus NL63
- ✓ Coronavirus OC43
- ✓ Human Metapneumovirus
- ✓ Human Rhinovirus/Enterovirus
- ✓ Influenza virus A
- ✓ Influenza virus B
- ✓ Parainfluenza virus 1
- ✓ Parainfluenza virus 2
- ✓ Parainfluenza virus 3
- ✓ Parainfluenza virus 4

- ✓ Respiratory syncytial virus
- ✓ Bordetella parapertussis
- ✓ Bordetella pertussis
- ✓ Chlamydia pneumoniae
- ✓ Mycoplasma pneumoniae

The potential SARS-CoV-2 infection will be reviewed by IDMC.

9.5.7.2 Detection of ELISA Antibodies against S1-RBD of SARS-CoV-2

Anti-S1-RBD antibody titers will be measured by ELISA kit. A dilution microplate is used to prepare the serum dilutions per SOP for test serum samples. Anti-S1-RBD antibody level is expressed as linear titers of an end point dilution for a test sample. SoftMax Titer Calculation Program (Molecular Devices Co.) is used to calculate the titers. For seroconversion detected by UBI SARS-CoV2 S1-RBD ELISA, it is defined as a 4-fold increase in antibody titer from baseline.

9.5.7.3 Detection of Antibody Titers Which Inhibit S1-RBD:ACE2 binding

Antibody titers for ability to inhibit S1-RBD:ACE2 binding will be measured by ELISA kit. A dilution microplate is used to prepare the serum dilutions per SOP. Antibody levels which inhibit S1-RBD:ACE2 binding are expressed in $\mu\text{g/mL}$ as titers for a test sample. SoftMax Titer Calculation Program (Molecular Devices Co.) is used to calculate the titers. Specimens that do not react in the test are considered with $< 1.6 \mu\text{g/mL}$ titer in this SARS-CoV-2 qNeu Ab ELISA.

9.5.7.4 Neutralizing Antibody Titers against SARS-CoV-2

Neutralizing antibody titers will be measured by CPE-based live virus neutralization assay using Vero-E6 cells infected with SARS-CoV-2. The study will be conducted in the BSL-3 lab at Academia Sinica, Taipei. The levels of SARS-CoV-2 virus specific neutralization titers are measured based on the principle of VNT₅₀ titer ($\geq 50\%$ reduction of virus-induced cytopathic effects). Virus neutralization titer of a serum specimen is defined as the reciprocal of the highest serum dilution at which 50% reduction in cytopathic effects are observed and results are calculated by the method of Reed and Muench. For seroconversion detected by live virus neutralization test, it is defined as a 4-fold increase in antibody titer from baseline.

9.5.7.5 Detection of antibody against SARS-CoV-2 antigens

Specific IgG antibodies against SARS-CoV-2 antigens derived from S2, N, and M proteins in the serum of subjects will be tested by UBI SARS-CoV-2 ELISA (antigen combinations) and Confirmatory SARS-CoV-2 ELISA (individual antigens). These ELISA tests can distinguish immune responses in infected versus vaccinated individuals.

9.5.7.6 Detection of T Cell Response

Human peripheral blood mononuclear cells will be used for evaluating vaccine-induced T cell responses. Antigen-specific interferon-gamma (IFN- γ) and IL-4 production will be measured by

ELISpot. Intracellular cytokine staining and flow cytometry will be used to evaluate CD4⁺ and CD8⁺ T cell responses. This assessment will be optional.

9.5.8 Communication and Use of Technology

This study may employ various methods, such as e-dairy, telephone, or other communication pathway, to contact with participants for record and maintain the study information. The communication items include but not limited to:

- Record 7-day solicited symptoms and 14-day skin allergic reaction after vaccination in reactogenicity e-diary
- Record unsolicited AEs or/and symptoms of COVID-19 on Day 8, Day 15, Day 22, Day 36, Day 43, Day 64, Day 71, Day 78, Day 85, **the day on 7 days after Visit 6 (only for subjects receiving 3rd dose)**, Day 253, and Day 309 using telephone communication
- Record regular surveillance for COVID-19 illness in e-dairy. A prompt on their smartphone device to regularly surveillance for signs and symptoms of COVID-19 every week after Day 57. If any potential symptoms for COVID-19 illness is reported, a telephone call will be made between site staffs and subjects.
- Unscheduled visit set-up or visit reminders

9.5.9 Appropriateness of Measurements

The immunogenicity and safety assessments planned for this study are generally recognized as reliable, accurate, and relevant to the diagnostic modality and underlying disease/condition.

9.6 Independent Data Monitoring Committee (IDMC)

The Independent Data Monitoring Committee (IDMC) will act in an expert, independent advisory capacity to monitor participant safety and evaluate the efficacy of UB-612 vaccine against COVID-19 in this study. The IDMC will consist of at least two physicians and one statistician. An IDMC meeting will be held at:

- (1) 1st time: when all adult immunogenicity data (350 evaluable young adults and 154 evaluable elderly subjects) for Day 57 are available
- (2) 2nd time: when at least half of core group subjects will be completed Day 85 safety follow up. Adolescence could be enrolled after 2nd IDMC meeting.
- (3) 3rd time: when all immunogenicity data for lot-to lot consistency of Day 57 are available.
- (4) 4th time: when 350 evaluable adolescents will be completed Day 57 safety follow up.

The meeting schedule might be adjusted based on the progress of recruitment. The IDMC meetings may also be held at any time point if any situations after vaccination meet the study stopping criteria or when the sponsor considers it necessary. Unscheduled IDMC meetings may also be held if any potential COVID-19 illness events or obvious situations for the deterioration the subject safety or study conduct occur.

Responsibilities of the IDMC include the following:

- ✓ Protect the safety and confidentiality of the study participants;

- ✓ Evaluate the quality and validity of the data generated in this study;
- ✓ Consider factors external to the study when relevant information becomes available, such as scientific or therapeutic developments that may have an impact on the safety of the participants or the ethics of the trial;
- ✓ Make recommendations to the Sponsor and the Principal Investigator (PI) concerning continuation, termination or other modifications of the study based on factors including overwhelming effectiveness, futility or safety issues;
- ✓ Make recommendations and assist in the resolution of problems reported by the PI;
- ✓ Assist sponsor by commenting on any problems with study conduct and/or data collection;
- ✓ Maintain confidentiality regarding the study outside the IDMC (including, but not limited to the investigators, IRBs, regulatory agencies, or sponsor) except as authorized by the IDMC.

Detailed description of the IDMC responsibilities, data reviewed, meeting process, considerations and policies will be described in a separate IDMC charter.

9.6.1 Overall Study Stopping Rules

The following stopping rules are in place for all subjects, based on review of AE data and e-diary reactogenicity data.

1. An SAE that is assessed by the investigator as possibly related, or for which there is no alternative, plausible, attributable cause.
2. A Grade 4 local reaction, systemic adverse event or fever that is assessed as possibly related by the investigator, or for which there is no alternative, plausible, attributable cause.
3. If any 3 subjects vaccinated with UB-612 (at any dose level) report the same or similar* severe (Grade 3) AE (including laboratory abnormalities), assessed as possibly related by the investigator, or for which there is no alternative, plausible, attributable cause.

* defined as same preferred term of current MedDRA

4. If a stopping rule is met, further dosing will be paused and the IDMC will determine whether dosing should resume.
5. If two of the same or similar *SAEs or Grade 4 local or systemic reactions occur, dosing will be suspended and both the IDMC and regulatory authorities will be consulted before resumption of dosing.

* defined as same preferred term of current MedDRA

In the event that a stopping rule is met, the following actions will be taken:

- The stopping rule will PAUSE randomization and administration of study vaccine at all dose levels and all treatment groups.
- The IDMC will review the relevant safety data.

- For all subjects already vaccinated, all other routine study conduct activities, including ongoing data entry, reporting of AEs, electronic diary completion, blood sample collection, and subject follow-up, will continue during the pause.
- Data from placebo recipients will not contribute to the stopping rules.
- Electronic diary data confirmed by the investigator as having been entered in error will not contribute toward a stopping rule.

Should the study be terminated prematurely, the sponsor will provide written notification to all investigators and regulatory authorities specifying the reason(s) for early termination. The investigator must inform the institutional review board (IRB)/independent ethics committees (IEC) promptly and provide the reason(s) for the termination. Previously dosed subjects will be assessed through all planned study safety visits.

10 STATISTICAL METHODS

The statistical planning and analysis of the trial will be performed by the designated contract research organization.

10.1 Statistical and Analytical Plans

A statistical analysis plan will be prepared and finalized prior to database lock of the study. The statistical analysis plan will include full details of all planned statistical analyses.

10.2 Sample Size Determination

Consider a 10% drop-out rate, around 3850 adult subjects in core group will be recruited and randomized to UB-612 vaccine 100 µg or placebo with 6:1 allocation rate and around 385 adolescents will be recruited for supplementary group and randomized to UB-612 vaccine 100 µg or placebo with same allocation ratio.

10.2.1 Sample Size for Safety Evaluation

For safety outcomes, the following table shows the probability of observing at least 1 SAE for a given true event rate of a particular SAE. For example, if the true SAE rate is 0.01%, with 2400 adult subjects, 600 elderly subjects, and 300 adolescent subjects received select vaccine dose, there are 21.3%, 5.8%, and 3.0% probabilities of observing at least 1 SAE. Overall, probability of observing at least 1 SAE is 25.9% with true SAE rate of 0.01% for all 3000 subjects received study vaccine in safety group.

True SAE Rate	N=300	N=600	N=2400	N=3000
0.001%	0.003	0.006	0.024	0.030
0.010%	0.030	0.058	0.213	0.259
0.100%	0.259	0.451	0.909	0.950

10.2.2 Sample Size for Lot-to-Lot Consistency

The sample size is driven by the objective to demonstrate the consistency of GMT ratio (GMTR) with the 3 consecutive manufacturing lots of the UB-612 vaccine. The clinical lot-to-lot consistency will be tested for the three pair-wise comparisons by computing the two-sided 95% CI on the GMTR. If all confidence intervals are within the pre-defined clinical limits of [0.5, 2.0], one can conclude that the lots are consistent.

Assume the expected GMTR of 1 and a value of 0.6 for the standard deviation (SD) of the decimal logarithmic transformation (log base 10) of antibody titers ($\log_{10}(\text{GSD})$) is about 0.2 to 0.6; refer to following table of the V-122 interim result). In order to have at least 90% power to achieve the lot-to-lot consistency, the estimated sample size should ensure beta less than 3.3% (Bonferroni adjustment of beta for 3 comparisons between 3 lots). With the parameters above it estimates a minimum evaluable sample size per lot of 115 subjects. Consider a 10% drop-out rate, a total of 396 subjects (132 subjects per lot) will be needed for ensuring overall lot-to-lot consistency with at least 90% overall power.

Table GSD and Logarithmic Transformation of Neutralizing Antibody Titers and Anti-S1-RBD Antibody Titers at Day 56

Antibody Titers	UB-612 10 µg		UB-612 30 µg		UB-612 100 µg	
	GSD	log10(GSD)	GSD	log10(GSD)	GSD	log10(GSD)
Neutralizing	3.286	0.52	2.438	0.39	1.670	0.223
Anti-S1-RBD	4.185	0.62	3.112	0.49	1.436	0.16

Note: Only first six subjects in 100 µg group had neutralizing antibody titer results at Day 56 until 2021-01-12

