7.4.6 Method of Assigning Subjects to Treatment Groups

The study vaccine and placebo will be randomly assigned to subjects. The randomized sequence of study treatments will be generated by an independent qualified biostatistician. The randomization schedule will be kept and maintained by the designated personnel before the study begins and until the database lock. The independent biostatistician prepares the randomization schedules via the SAS software (9.4 or higher version).

For core group, around 3850 participants will be randomly assigned to UB-612 vaccine 100 µg or placebo with a 6:1 randomization ratio (vaccine: placebo) by block randomization. In addition, a total of 966 evaluable subjects including 812 evaluable young adult and 154 evaluable elderly subjects from core group will be apportioned to immunogenicity and **lot-to-lot group** with a randomization ratio of 6:1 to UB-612 vaccine (696 evaluable young adult subjects and 132 evaluable elderly subjects) and placebo (116 evaluable young adult subjects and 22 evaluable elderly subjects). Furthermore, the 396 evaluable young adult subjects in immunogenicity group assigned to UB-612 vaccine will be allocated to 3 specified vaccine lots with a 1:1:1 ratio for evaluating the lot-to-lot consistency. Therefore, a total of 462 evaluable young adult subjects of immunogenicity group will be randomized to 3 vaccine lots and placebo with a ratio of 2:2:2:1 (vaccine lot 1: vaccine lot 2: vaccine lot 3: placebo).

In supplementary group, around 385 adolescent subjects aged from 12 to 18 years old will randomly receive UB-612 vaccine 100 µg or placebo with allocation rate 6:1, too.

Eligible subjects will receive a random number at randomization in form of a sealed envelope. The authorized unblinded dispenser(s)/administrator(s) who involve in the treatment of vaccine/placebo will be required to open the envelope and administer the corresponding treatment assigned by the envelope. For any reason that a subject withdraws from the study prematurely after the randomization, his/her randomization number will not be reused. The next eligible subject will receive the lowest available randomization number.

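### V-205: at the planning SD of 0.6, the stated minimum of 115 evaluable subjects per lot gives about 84% overall power, not 90%, and the 396 is labelled both drop-out-inflated and evaluable

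*Supplement*

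**What the plan says.** V-205 Section 10.2.2, repeated in the Synopsis, sizes the lot comparison. Consistency is to be "tested for the three pair-wise comparisons by computing the two-sided 95% CI on the GMTR", with the rule "If all confidence intervals are within the pre-defined clinical limits of [0.5, 2.0], one can conclude that the lots are consistent". The planning values are a true GMT ratio of 1, an SD of 0.6 on the log10 scale, overall power of at least 90%, and beta below 3.3% for each of the three comparisons. The section concludes "With the parameters above it estimates a minimum evaluable sample size per lot of 115 subjects" and, after a 10% drop-out allowance, "a total of 396 subjects (132 subjects per lot) will be needed for ensuring overall lot-to-lot consistency with at least 90% overall power".

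Section 7.4.6 uses the same number with a different label: "Furthermore, the 396 evaluable young adult subjects in immunogenicity group assigned to UB-612 vaccine will be allocated to 3 specified vaccine lots". It then forms 462 subjects at 2:2:2:1 with placebo and also calls these evaluable, as do the Synopsis and Sections 7.1 and 7.3. Section 10.6.2 confirms the analysis: a Student's t interval on the log10 difference for each pair, two-sided 95%.

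**The concern.** At a true ratio of 1, a confidence interval can miss the lower limit or the upper limit with equal probability. The 3.3% allowed per pair must therefore cover both ways of failing. A formula that charges all of it to one limit returns too small a sample.

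The two labels on 396 add to this. If 396 is what remains after losses, the extra subjects make up the shortfall. If 396 is what is randomized, they do not. Whether the claim of 90% overall power is true therefore depends on wording that the protocol leaves unresolved. Lot consistency is a secondary endpoint with a formal pass/fail rule, and its interim report is part of the EUA dossier, so the stated power should hold under its stated assumptions.

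**Working it through.** **Inputs (V-205 Section 10.2.2).** Margin log10(2) = 0.301; SD 0.6, so variance 0.36; true difference 0; two-sided 95% CI, i.e. 0.025 in each tail, z = 1.960; beta per pair 10%/3 = 3.33% (the text rounds to 3.3%).

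**Reproducing 115.** With all of beta at one limit, z(1 − 0.0333) = 1.834:

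n = 2 × 0.36 × (1.960 + 1.834)² / 0.301² = 114.4, so 115 per lot (114.6 with beta 3.3%, also 115).

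The protocol does not print its formula. A 90% interval with beta split also lands close, at 2 × 0.36 × (1.645 + 2.128)² / 0.301² = 113.1, so 114, but that contradicts the stated 95%.

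**Beta split over the two limits.** z(1 − 0.0333/2) = 2.128:

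n = 2 × 0.36 × (1.960 + 2.128)² / 0.301² = 132.8, so 133 per lot (133.04 with beta 3.3%, so 134).

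**Power actually delivered at SD 0.6.** Power per pair comes from the t-based two one-sided tests, integrated over the sample variance. Overall power comes from 2,000,000 simulated trials requiring all three pairwise 95% t intervals to lie within the limits.

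| Evaluable per lot | Per pair | All three pairs |
|---|---|---|
| 115 | 93.3% | 83.9% |
| 119 (132 less 10%) | 94.2% | 86.0% |
| 129 | – | 90.0% |
| 132 | 96.4% | 91.0% |
| 134 | 96.7% | 91.6% |

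At 115 the per-pair failure probability is 100 − 93.3 = 6.7%, twice the 3.3% intended. The Bonferroni guarantee is then 1 − 3 × 0.0675 = 79.8%. The joint figure is higher, at about 84%, because the three comparisons share lots.

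**The drop-out step.** 115 / 0.9 = 127.8, so 128 per lot (384 in total), not 132. Reaching 132 from 115 implies a loss of 1 − 115/132 = 12.9%. If 132 per lot are randomized and 10% are lost, 132 × 0.9 = 118.8 remain.

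**Dependence on the SD (overall power at 115 per lot).** 0.39: above 99.9%. 0.52: 95.8%. 0.55: 92.4%. 0.60: about 84%. 0.62: 79.7%.

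The table in Section 10.2.2 gives log10 SDs for neutralizing antibody of 0.52, 0.39 and 0.223 at 10, 30 and 100 µg, the last from six subjects. Table 5-1 of the V-123 protocol has all 20 subjects at 100 µg on Day 56, with 95% CI 70.764 to 149.836. The half-width is log10(149.836/70.764)/2 = 0.163, so SD = 0.163 × √20 / 2.093 = 0.348. At that SD, power with 115 per lot is near 100%.

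**The case against.** The strongest reply is that 115 is only an intermediate figure. Section 10.2.2 itself ends at 396, and every operative statement about the subset uses 396 or 462 and calls them evaluable. On that reading the design has about 91% overall power even at SD 0.6. This stands as far as it goes. It does not repair the sentence giving 115 as a sufficient minimum, and it requires setting aside the drop-out wording that introduces 396.

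The second reply is that SD 0.6 is the top of the range the protocol quotes. No neutralizing SD in its table brings 115 per lot below 90%; only the anti-S1-RBD value at 10 µg (0.62) exceeds 0.6, and that is neither the endpoint nor the dose. This also stands, and it limits the practical consequence. A power statement should still be true at the planning value chosen for it.

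Two stronger inferences are tempting and are not supported:

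- **That the trial as designed is underpowered for lot consistency.** This holds only at SD 0.6, and only at 115 evaluable or if 396 is the randomized count. A power shortfall also does not raise the chance of a false claim of consistency.
- **That the lot subset could be closed early at 115 per lot.** Section 10.2.2 finishes at 132 per lot, Section 7.4.6 assigns subjects from a pre-generated schedule, and the third interim analysis waits for all the lot-consistency data at Day 57.

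**Conclusion.** The stated minimum is wrong under its own assumptions. With a true ratio of 1, log10 SD 0.6 and all three two-sided 95% CIs required within 0.5 to 2.0, 115 evaluable per lot gives about 93% per pair and 84% overall. The evaluable size needed is 133 to 134 per lot by the protocol's own Bonferroni route with beta split, or about 129 by joint simulation.

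Separately, 396 cannot be both the drop-out-inflated count and the evaluable count. Overall power is about 91% on the evaluable reading and about 86% on the randomized reading with 10% loss. The documents do not settle which was meant.

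This is an error in the written justification. Given the SD of about 0.35 in the full 100 µg data, it is unlikely to affect the consistency result.

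**What to change.** In V-205 Section 10.2.2 and the Synopsis:

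- State the formula, and either replace 115 with 133 to 134 evaluable per lot (split-beta Bonferroni) or about 129 (joint simulation, cited as such), or state that 132 evaluable per lot gives about 91% overall power at SD 0.6.
- Reconcile Sections 10.2.2 and 7.4.6 by saying whether 396 and 462 are evaluable or randomized, and give the other count as well. If 396 is evaluable, a 10% loss requires 132/0.9 = 146.7, so 147 per lot or 441 vaccine recipients randomized. If 396 is randomized, about 396 × 0.9 = 356 are evaluable, and the overall power should be restated as about 86% (84% at 115 evaluable).
- Correct the drop-out step, since 115 inflated for 10% is 128 per lot.

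Simply deleting the drop-out wording would not be enough, because it would leave the subset without a randomization target.

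The cost is protocol and SAP wording. The subset is drawn from the 3850 adults already planned, so total enrolment need not grow. Keeping 396 evaluable would mean immunogenicity blood draws and live-virus assays for up to 441 − 396 = 45 further vaccine recipients, plus the matching placebo subjects.

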10.3 Analysis Populations

Enrolled Population

Enrolled Population includes subjects who have a signed ICF.

Randomized Population

Subjects who are assigned a random number be regarded as Randomized Population.

Evaluable Immunogenicity Population

Evaluable Immunogenicity Population will consist of all eligible randomized subjects who are assigned to lot-to-lot and immunogenicity group, receive two vaccinations within the predefined window, have a valid immunogenicity result at visit 4 (Day 57), have no major protocol deviations or protocol deviations having impact on immunogenicity data. Evaluable Immunogenicity Population will be regarded as primary population for immunogenicity evaluation on primary and secondary immunogenicity endpoints except lot-to-lot consistency.

Evaluable Lot-to-Lot Population

Evaluable Lot-to-Lot Population is a subset of Evaluable Immunogenicity but only includes subjects who are assigned to lot-to-lot consistency group and have immunogenicity determination at Day 57. Evaluable Lot-to-Lot Population will be used for evaluating lot-to-lot consistency only.

Evaluable Efficacy Population

All eligible randomized subjects who receive two vaccinations within the predefined window and have no major protocol deviations or protocol deviations having impact on immunogenicity data will be the Evaluable Efficacy Population. Evaluable Efficacy Population will be used to evaluate vaccine efficacy in exploratory analysis.

Available Immunogenicity Population

Available Immunogenicity Population will consist of all eligible randomized subjects who receive at least one vaccination, and have at least one post immunogenicity data determination. Available Immunogenicity Population will also be used to the immunogenicity evaluation except lot-to-lot consistency.

Evaluable Booster Population

All eligible randomized subjects who receive third dose of UB-612 within the predefined window and have no major protocol deviations or protocol deviations having impact on immunogenicity data will be the Evaluable Booster Population. Evaluable Booster

Population will be used to explore the immunogenicity evaluation after the booster vaccination.**Safety Population**

Safety Population (SAF) will consist of all subjects who received at least one vaccination. The Safety Population is for safety evaluation in analysis.

